1 PROTOCOL SUMMARY

1.1 SYNOPSIS

Title:	An Integrated Two-Way Communication and Near-Real-Time Sensing System to Detect and Modify Daily Inactivity among Adults Over Age 60
Grant Number:	5P30AG048785-07
Study Description:	The objective is to test if Companion, an Integrated Two-Way Communication and Near-Real-Time Sensing System, improves and sustains overall daily free-living activity and sedentary behavior in adults over 60 y. The central hypothesis is that Companion will improve overall daily free-living activity and sedentary behavior in adults >60 y and thereby improve their health.
Objectives*:	
Primary Objective: Determine if Companion improves free-living activity and sedentary behavior and sustains this change in adults >60y. In this RCT (n=46), both treatment and control groups will engage in a 16-week supervised exercise program and then be followed-up after 24 weeks.^{1,2} Companion will be deployed in the treatment group (n=23) only. Primary outcomes are daily total and bouts of physical activity and sedentary time.
 
Exploratory Objective: Explore if supplementing supervised exercise with Companion further improves and sustains cardiometabolic health, body composition, cognition, and psychosocial outcomes.

Endpoints*:	
Primary Endpoint: Physical activity and sedentary time: Daily total and bouts
 
Exploratory Endpoints: Anthropometrics; Plasma glucose; HbA1C; Insulin; Lipids; Lean and fat mass; Physical function; Muscular and aerobic fitness; Cognition; perceptions of competence related to health behavior; Autonomy support (from companion); Autonomous motivation (for physical activity); Relatedness (to the Companion); General satisfaction.

Study Population:	N= 46, gender- NA, age >60 y, demographic group- older adults; general health status- healthy; geographic location- Boston and surrounding neighborhoods.
Phase* or Stage:	1A
Description of Sites/Facilities Enrolling Participants:	The Human Performance and Exercise Science (HPES) Laboratory is located in the Behrakis Health Science Center at Northeastern University, which will be the sole site for the study. Participants who do not prefer to have their measurements conducted at their residence will come to the lab to have measurements completed. The study is not intended to include sites outside of the United States.

Description of Study	The study intervention consists of wearable sensors integrated with the smartphone to develop a behavior-aware, virtual “Companion” that uses a “human-in-the-loop” approach to enable meaningful two-way communication. Companion builds rich models of typical behavior using sensors and context sensitive ecological momentary assessment (CS-EMA) to deliver intervention components and behavior change strategies using socially engaging, contextually salient, and tailored text-message conversations in near-real-time. The duration of the intervention is 4 months.
Study Duration :	Estimated time (in months) from when the study opens to enrollment until completion of data collection is 6.5 months.
Participant Duration:	Time for each individual participant to complete all study-related tasks is 6.5 months.

1.2 SCHEMA

1.3 SCHEDULE OF ACTIVITIES

	Pre-screening (Pre-consent)	Measurement 1 Day 1	Virtual visit Day 7-14	Measurement 2 Day 120-130	Measurement 3 Day 240-250
Review Eligibility	X				
Informed Consent		X			
Demographics		X			
Outcome Evaluation		X		X	X
Randomization		X			
Control & Experimental Interventions					►
Counselling			X		
Adverse Events Reporting		X	X	X	X

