4 STUDY DESIGN

4.1 OVERALL DESIGN

Hypothesis (Aim 1): The treatment group will show greater improvements in daily activity and sedentary behavior outcomes than controls after 16 and 24 weeks.

Hypothesis (Aim 2): The treatment group will show greater improvements in health and psychosocial outcomes than controls after 16 and 24 weeks.

Phase: 1A.

Design: Randomized control trial

Participant assignment: 1:1 Simple Randomization conducted by graduate assistant

Number of study group: 2 (control/treatment); intervention period= 4 months; follow-ups after 4 and 6 months.

Number of sites= Single site trial.

Name and description of intervention: Companion; An integrated system of wearable sensors and the smartphone. It is a behavior-aware, virtual “Companion” that uses a “human-in-the-loop” approach to enable meaningful two-way communication. Companion builds rich models of typical behavior using sensors and context sensitive ecological momentary assessment (CS-EMA) to deliver intervention components and behavior change strategies using socially engaging, contextually salient, and tailored text-message conversations in near-real-time.

Description of control group: This group will not receive the Companion, which will be the only difference with the treatment group. I.e., the control group will receive standard treatment– the supervised training program and an exercise prescription for those days without supervision.

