Control Group: This group will not receive the Companion, which will be the only difference with the treatment group. I.e., the control group will receive standard treatment– the supervised training program and an exercise prescription for those days when they are on their own. This will be done on the two days when control group participants meet face-to-face with the trainer for supervised training.

Primary Outcomes: Total duration and number of bouts of: (i) light and moderate-to-vigorous physical activity and (ii) sedentary behavior measured over a period of one week using accelerometry.^{38,39} Week-long measures will be made at baseline, and weeks 16 and 24.

Exploratory Outcomes: Cardiometabolic health: Plasma glucose, HbA1C, insulin, and lipids. Body composition: lean and fat mass. Physical function. Muscular and aerobic fitness. Cognition.⁴² Perceptions of competence related to health behaviors. Autonomy support (from companion). Autonomous motivation (for physical activity). Relatedness (to the Companion). General satisfaction.

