8 STUDY ASSESSMENTS AND PROCEDURES

8.1 ENDPOINT AND OTHER NON-SAFETY ASSESSMENTS

Table 1. Measures in Laboratory or Home

Measure	Measurement 1: Baseline (1-2 h)	Measurement 2: Follow-up 1 (4 months) (1-2 h)	Measurement 3: End of study (6 months) (1-2 h)
Heart rate and blood pressure	✓	✓	✓
Anthropometrics (Height, weight, waist, and hip circumference)	✓	✓	✓
Body composition (Bioelectrical impedance)	✓	✓	✓
Fasting blood glucose, and lipid profile	✓	✓	✓
Cognitive tests	✓	✓	✓
Physical function tasks	✓	✓	✓
Muscular and aerobic fitness	✓	✓	✓
Other			✓

The following tests and procedures will be conducted in the numbered order. All measurements will be made in a secure location to ensure privacy.

1. **Resting heart rate and blood pressure:** Heart rate and blood pressure will be measured using an automatically inflatable blood pressure arm cuff and monitor. These measures will be conducted in triplicate after a rest of 5 minutes between each measure.
2. **Anthropometrics:** Height and weight will be measured using a stadiometer and a standard digital weight scale, respectively, and circumferences will be measured by a trained research staff member using a measuring tape (in triplicate).
3. **Body composition:** Whole body percent fat and lean mass will be measured using Bioelectrical Impedance (BIA) and will be conducted by trained research staff. During the test, the participant will step bare feet on an electronic scale and hold handheld conduction electrodes. A weak electric current will flow through the body and the voltage is measured in order to calculate impedance of the body and thereby, the % of body fat and lean mass. The test will be completed within 30 s. The participant will not feel anything, and this test is similar to stepping on a weighing scale.
4. **Blood glucose and lipid profiles:** We will measure this using finger-stick blood analyses with a CardioChek Plus device (PTS Diagnostics). The CardioChek Plus is a certified fast, accurate and efficient portable analyzer capable of obtaining a full lipid profile and glucose readings in 90 seconds from a finger stick strip blood sample (15 – 40 micro Liters). The participant's blood will not be stored, as the finger stick analyses are immediate, and the measuring strips are discarded appropriately after the test.

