(ii) Aerobic Fitness- We will assess aerobic fitness using the 6-minute walk test. This is a simple test that requires no specialized equipment and only requires the participant to walk on a flat, hard surface for a period of 6 min. The total distance walked during this duration is measured using a measuring wheel.

8. Other: (i) 7-14 days after baseline, participants in the general exercise intervention group will have a virtual 30-min face-to-face counseling session with the researchers on: i) benefits of reducing sedentary behavior and increasing physical activity, and ii) various strategies to decrease workplace and home sedentary behaviors and initiate a physically active lifestyle.

(ii) Participants in the lifestyle physical activity intervention group will have a virtual 60-min face-to-face counseling session via a HIPAA complaint ZOOM session. This session will include the same components received by the general exercise intervention group supplemented with an additional 30-min of conversation to further personalize his or her physical activity prescription plan and create goals related to physical activity and sedentary behavior lifestyle choices. During this time the researcher will ask the participant in the lifestyle physical activity intervention group questions about his or her schedule, preferences, health-related behaviors, and other behaviors related to work schedule, hobbies/leisure interests, family dynamics, home and work environment, means of daily transportation, etc. that can be used to help support the participant towards achieving his or her physical activity and sedentary behavior lifestyle goals.

(iii) After study completion, participants will be asked to complete a follow-up interview in person during the end of study follow-up (month 6). The interview will take no longer than 15-20 minutes. The conversations may be recorded only with the participant's permission. Once the audio recordings are transcribed, the audio recordings will be immediately destroyed.

Table 2. Self-completed Measures (1 – 1.5 hours)

Measure	Baseline	Month 4 follow up	Month 6 follow up
General Health and Health Related Quality of Life	✓		
Perceived Competence Scale for Participating in	✓	✓	✓

Regular Physical Activity			
Short Health Care Climate Questionnaire	✓	✓	✓
Exercise Self-Regulation Questionnaire	✓	✓	✓
Basic Need Satisfaction in Relationships Scale	✓	✓	✓
Diet	✓	✓	✓
Activity Monitoring	✓	✓	✓

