After completing the measurements in Table 1, participants will be given questionnaires and small activity monitors. It will take approximately 1-1.5 hours to complete the questionnaires. A research staff member will collect the questionnaires from the participant after a week.

1. Perceived Competence Scale for Participating in Regular Physical Activity: This is a 4-item questionnaire that assesses a participant's feelings of competence about engaging in physical activity.
2. Short Health Care Climate Questionnaire: This questionnaire has 6 items that assess a participant's perceptions of the degree to which the companion is supportive of autonomy; i.e., that the Companion considers the participants perspective and provides appropriate and meaningful feedback and opportunities for choice.
3. Exercise Self-Regulation Questionnaire: This is a 31- item self-report to measure the ability of the participant to regulate behavior to achieve one's goals
4. Basic Need Satisfaction in Relationships Scale: This scale addresses need satisfaction in general in one's life. It has 21 items assessing the three needs for competence, autonomy, and relatedness.
5. Diet: The participant will report frequency and portion size of foods consumed during the past month from a list of 70 commonly consumed food items on a questionnaire.
6. Activity Monitoring: physical activity measurement will be conducted in two ways. Firstly, using a thigh worn monitor. This measurement will be conducted for a period of 7-days at baseline and after 4 and 6 months. For this measurement the participant will wear 1 small lightweight (\approx 0.5 ounces) activity monitor (activPAL3TM, PAL Technologies, Glasgow, UK; product specs: <http://www.palt.com/pals/>) on his or her dominant thigh, which will be adhered to his or her skin using a hypoallergenic medical grade tape (3M TegadermTM Film, 3M, Minneapolis, MN; product specs: https://www.3m.com/3M/en_US/company-us/all-3m-products/~/3M-Tegaderm-Transparent-

Film-Dressing/?N=5002385+3293321979&preselect=3293786499&rt=rud). During the 7-day measurement periods, the participant will also complete a record of times the monitors were removed from his or her person. These thigh sensor data will not be transmitted wirelessly. The researchers will download the data from the devices upon collecting them from the participants. The researchers will go to the participant's office/home to collect these.

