Secondly, during the entire duration of the study, including the three 7-day physical measurement periods with the thigh activity monitor, the participant will be asked to wear a small wrist sensor (~ 0.64 ounces) [(i). general exercise group: ActiGraph GT9X Link; (ii). lifestyle physical activity group: CentrePoint Insight Watch, Actigraph Corp. LLC, Pensacola, FL; product specs for GT9X available at <https://www.actigraphcorp.com/actigraph-link/> and for Insight Watch available at <https://www.actigraphcorp.com/cpiw/>). These devices will be worn on the non-dominant wrist on a watchstrap.

Participants in the general exercise intervention group will receive a new GT9X monitor every 1-4 weeks to ensure the devices always have enough battery life to measure physical activity. The researchers will go to the participant's preferred location (office or home) to provide a new sensor. These wrist sensor data will not be transmitted wirelessly. The researchers will download the data from the devices upon collecting them from the participants.

Participants in the lifestyle physical activity intervention group will receive an Insight watch that is capable of passively uploading motion data so that the researchers may get an understanding of his or her daily movement patterns. This information is confidential and will be used for research purposes only. No other data besides data about the participant's movement is gathered using any of the sensors. The researchers will come to the participant's office or home at the beginning of the study to install the data capturing systems (i.e., data transfer hubs). The decision on the location to install the hub (i.e., home vs office) will be determined in consultation with the participant. The location will be where the participant spends the most part of the week during the waking day. These data hubs are small devices that require a power source connection to communicate wirelessly with the device the participant will be wearing and relay data to the researcher. The researchers will uninstall the data hubs following completion of study participation either after the month 6 follow up or prior to that should the subject decide to drop out of the study. Please see the attached PDF detailing the data capturing and transmission process.

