9 STATISTICAL CONSIDERATIONS

9.1 STATISTICAL HYPOTHESES

- Primary Endpoint(s): Daily total and bouts of physical.

The treatment group using Companion will show greater improvements in daily activity and sedentary behavior outcomes than controls after 16 and 24 weeks. Alternatively, our null hypothesis is that there will be no difference in the treatment group for daily activity and sedentary behavior outcomes after 16 and 24 weeks.

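### The schedule of activities puts the final primary-outcome visit at Day 240-250, about 10-12 weeks after the week 24 that the hypotheses test and about 8-10 weeks after the month 6 used in the procedures

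*Combined protocol and SAP*

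**What the plan says.** Section 1.3 marks an outcome evaluation at three visits: Day 1, Day 120-130, and "Measurement 3 Day 240-250". The other statements about the last of these fall into four groups.

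- **Week 24.** Section 9.1 states the primary hypothesis as "The treatment group using Companion will show greater improvements in daily activity and sedentary behavior outcomes than controls after 16 and 24 weeks". Section 4.1 gives the same two time points for both aims. Section 6.1.1, which defines the primary outcomes, says "Week-long measures will be made at baseline, and weeks 16 and 24".
- **Month 6.** Section 4.1 also says "follow-ups after 4 and 6 months". In section 8.1, Table 1 names Measurement 3 as the 6-month end-of-study visit, Table 2 has a month 6 column, and the exit interview is set for month 6. For the thigh monitor, section 8.1 says "This measurement will be conducted for a period of 7-days at baseline and after 4 and 6 months". The data hubs come out "following completion of study participation either after the month 6 follow up", or sooner on dropout. Section 5.5 ties payment to month 6.
- **6.5 months.** Section 1.1 gives this as the time a participant needs to finish every study task.
- **24 weeks, starting day not stated.** The synopsis describes a 16-week exercise programme with follow-up after 24 weeks and does not say from when the 24 weeks run.

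Section 8.1 ends the daily coaching at the month-4 follow-up. No section mentions month 8 or explains Day 240-250.

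**The concern.** One primary time point has three incompatible dates, and the outlier is in the table that staff use to book visits. The primary objective is that Companion improves behaviour and that the change lasts. With coaching over at month 4, Measurement 3 is the only defined primary-outcome assessment that can answer the second half.

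The mixed models in section 9.4 name no visit days, so they would estimate the contrast on whatever day the visit took place. If section 1.3 is followed, a result collected around week 35 would be reported against a hypothesis about week 24. Persistence for about four months after the first follow-up is a different claim from persistence for about two. Participants would also be kept in the study beyond the stated 6.5 months. A visit made at the wrong time cannot be corrected at analysis.

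**Working it through.** **Inputs.** Visit days are from section 1.3, weeks 16 and 24 from 4.1, 6.1.1 and 9.1, months 4 and 6 from 4.1 and 8.1, and 6.5 months from 1.1. A week is 7 days and a month is taken as 30.44 days; other month lengths are tried below.

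**Does the rule reproduce the schedule's other follow-up?** Yes. 4 × 30.44 = 121.8, which lies inside Day 120-130. The schedule's day count therefore agrees with the text at Measurement 2.

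**Measurement 3.** 240/7 = 34.3 and 250/7 = 35.7 weeks; 240/30.44 = 7.9 and 250/30.44 = 8.2 months.

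| Stated time | Day | Gap to Day 240-250 | In weeks |
|---|---|---|---|
| Week 24 | 24 × 7 = 168 | 72-82 days | 10.3-11.7 |
| Month 6 | 6 × 30.44 = 182.6 | 57.4-67.4 days | 8.2-9.6 |
| 6.5 months | 6.5 × 30.44 = 197.8 | 42.2-52.2 days | 6.0-7.5 |

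None of the three falls in the window. Eight months does: 8 × 30.44 = 243.5.

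**Interval from first to final follow-up.**
- Schedule: (240 − 130)/7 = 15.7 to (250 − 120)/7 = 18.6 weeks.
- Weeks 16 to 24: (168 − 112)/7 = 8.0 weeks.
- Months 4 to 6: (182.6 − 121.8)/7 = 8.7 weeks.
- Ratio: 15.7/8.7 = 1.8 to 18.6/8.0 = 2.3.

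**Could a different starting day explain it?**
- *From the virtual visit at Day 7-14.* Week 24 becomes Day 175-182, leaving 240 − 182 = 58 to 250 − 175 = 75 days (8.3-10.7 weeks). Month 6 becomes Day 189.6-196.6, leaving 43.4-60.4 days (6.2-8.6 weeks).
- *24 weeks from the end of the 16-week programme*, one reading of the synopsis. (16 + 24) × 7 = Day 280, which is 30 days after the window closes.

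**Sensitivity to day counting.** With 30-day months the gap to month 6 is 8.6-10.0 weeks and the overrun past 6.5 months is 6.4-7.9 weeks. With 31-day months they are 7.7-9.1 and 5.5-6.9 weeks. Counting Day 1 as elapsed day 0 takes one further day off each gap, so the smallest overrun is 5.4 weeks. The 7-day monitor wear begins after the visit measurements and would add about a week to the overrun.

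**The case against.** The strongest counter-argument concerns what is at stake. Section 8.1 asks both arms to wear a wrist sensor for the whole study, and section 9.4.2 describes the primary endpoint only as coming from body-worn sensors. On that reading, activity data would exist at week 24 and at month 6 even if the visit took place at Day 240, and Measurement 3 would not be the only post-coaching evidence. It is true that such data would exist. They are not the defined primary outcome, however. Section 6.1.1 specifies week-long measures at baseline and two follow-ups, and section 8.2 says the primary outcome is measured with sensors taped to the skin, which in section 8.1 is the thigh monitor. The wrist devices also differ between the arms.

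A second argument is that this is a slip in one column heading, set against nearly uniform text, with no bias between arms and no effect on the sample-size calculation. A slip is plausible, and it is right that neither the comparison nor the sample size depends on this date. The error is nonetheless in the operational table, the documents do not say which timing is meant, and the two alternatives in the text themselves differ by about two weeks (182.6 − 168 = 14.6 days).

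Three smaller points stand. The overrun past 6.5 months is best given as about 6 weeks or more, because some day-count conventions bring its minimum slightly below 6. The schema in section 1.2 could not be seen in the text reviewed; it might show the intended timing but would not remove the written conflict. Measurement 2 is a lesser matter: Day 120-130 fits month 4, and week 16 counted from the Day 7-14 visit (Day 119-126) overlaps it.

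**Conclusion.** The concern holds. The Day 240-250 window contradicts every other dated statement of the final assessment: by 10.3-11.7 weeks against week 24, 8.2-9.6 weeks against month 6 and 6.0-7.5 weeks against the 6.5-month participation. It roughly doubles the interval over which persistence is judged. The week-24 gap needs only the documents' day numbers, with Day 1 as the origin; the other two also need a month length, and no reasonable choice closes them. The documents do not show which timing is intended, and this review takes no position on that. The consequence is a wrong or ambiguous time point and label for the sustained-change result. It is not a bias between arms. It should be settled before any Measurement 3 visit is booked.

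**What to change.** Choose one anchor, for example randomisation, and one target day with a window for each assessment. Use them in sections 1.1, 1.3, 4.1, 6.1.1, 8.1 and 9.1, and align the payment text in 5.5.

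- If Day 240-250 is intended, restate the hypothesis and analysis time point as about week 35 and lengthen the participant duration.
- If week 24 or month 6 is intended, correct the Measurement 3 column and say which of the two it is.
- In either case, say from when the synopsis's 24 weeks run, and whether Measurement 2 stands for week 16 or month 4.
- If some final visits have already taken place, report their actual study days by arm and label the result by those days.

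As a separate minor correction, the overall study duration in 1.1 equals one participant's duration (6.5 months) and should allow for accrual.

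The cost is protocol wording and one schedule column, with no extra participants or procedures.

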2.3 RISK/BENEFIT ASSESSMENT

2.3.1 KNOWN POTENTIAL RISKS

There is a risk of physical injury during exercise, particularly if participants have little to no previous experience. Fatigue and muscle soreness may also occur in participants who do not normally engage in physical activity. Exercise is associated with a very small risk of serious medical complications including heart attack and sudden death, although this risk is particularly small in healthy older adults.

There is a potential risk of breach of confidentiality that is inherent in all research protocols.

Some inconvenience and or anxiety may occur due to time required to complete formal rating scales and questionnaires. The cognitive assessments impose some risk of emotional discomfort. Fatigue associated with performing the cognitive tasks- These items will be scored within 24 hours of completion by the subject.

Participants may experience red skin or discomfort from wearing body-worn sensor devices for an extended period of time.

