Supervised Exercise Program: For the first 16 weeks, all participants will engage in ~45 to 60 min of aerobic, strength, flexibility and balance training, twice/week.^{29,35} Participants will either visit Northeastern's Exercise Science Lab for supervised personal training or engage virtually over Zoom during the training session. The lead trainers will be an exercise physiologist or a trained graduate student. After the session, the trainer and participant will outline goals and prescription plan for the days prior the next training session and those to be performed by the participant on their own. The plan

will be based on guidelines from the American College of Sports Medicine.^{36,37} Supervised training sessions for the two groups will be scheduled on different days and allocation of participants to a trainer will be at random.

Treatment Group: This group will receive the Companion. Communication during weeks 1 to 4, will focus on gathering information on the participant's motivations, preferences, habits, contexts, and usual behavior patterns to build a typical behavior model for the participant. We expect a decreasing level of change in behavior models that are built using information accrued incrementally over these 4 weeks.²³ Companion will monitor ongoing and recent behavior, communicate with the participant (if necessary) to deliver contextually salient intervention strategies. Additionally, there will be a fixed Companion-initiated communication in the early evening (~4 to 6 pm) to discuss the achievement of that day's goals and prescribe strategies to achieve pending goals.

The nature of the first communication the next morning will be based on participant performance during all waking hours of the preceding day- e.g., encouraging, problem-solving. This is possible because the participant will be instructed to continuously wear the wrist device, which stores motion data in its internal memory. These data will be downloaded to Companion and analyzed.

Regular interaction will enable a corresponding incremental personalization of communication based on knowledge of each participant's communication style and personality. Similarly, such frequent interaction will also enable an incremental knowledge of the participant's changing physical ability and activity preferences, which will facilitate a corresponding increase in personalizing activity prescription.

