Participants in the lifestyle physical activity intervention group will also have the battery life of his or her wrist-worn activity monitor frequently monitored by the researchers via the passive data transfer system. When the researchers detect that the device has a low battery (battery life is approximately 2-3 weeks), the participant will be prompted to schedule a time to receive a new device from the researchers. The researcher will go to the participant's office or home to collect the monitor and return it charged by the next day to commence the daily physical activity measurement.

We will encourage participants in both groups to wear the sensors as much as possible so that: 1) we may be able to understand the differences in daily/weekly physical behavior change effects between the two intervention approaches, and 2) we may be able to tailor daily recommendations of participants in the lifestyle physical activity intervention group to maximize and maintain his or her gains and to help meet his or her goals. Participants may remove the sensors for brief intervals throughout the day (e.g., for showering). The researchers may provide participants in the lifestyle physical activity intervention group with retrospective feedback of his or her physical activity measurements via text-message frequently (4 to 7 times a day at intervals of 1 to 4 hours between 7

am – 10 pm), following the virtual session (Table 1 #8). To reiterate, daily retrospective feedback (health coaching) will last for 4 months, concluding at the month-4 follow up.

Change in outcome measurements will be provided to participants after the follow up at month 6, when requested by the participant.

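### Adverse events are scheduled for enquiry at four contacts only, leaving 106–123 days without one over most of the exercise programme, and no safety summary is planned

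*Combined protocol and SAP*

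**What the plan says.** Protocol 1.3 has a single row for safety collection, "Adverse Events Reporting X X X X". The ticks fall under Measurement 1 (Day 1), "Virtual visit Day 7-14", "Measurement 2 Day 120-130" and "Measurement 3 Day 240-250".

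Section 6.1.1 states that for the first 16 weeks "all participants will engage in ~45 to 60 min of aerobic, strength, flexibility and balance training, twice/week". Section 2.3.1 names exercise injury, soreness, fatigue and rare cardiac events as risks. For the sensors it adds: "Participants may experience red skin or discomfort from wearing body-worn sensor devices for an extended period of time".

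The thigh monitor is taped on for 7 days at each of the three measurement times. Section 8.1 gives the order: "After completing the measurements in Table 1, participants will be given questionnaires and small activity monitors". Staff later visit to collect the devices.

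Section 8.1 also says that the Companion arm may be sent feedback by text "4 to 7 times a day at intervals of 1 to 4 hours", from the virtual session until the month-4 follow-up. It provides for wrist-sensor exchanges in both arms: every 1–4 weeks for controls, and when the battery runs low (about 2–3 weeks) in the Companion arm.

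Section 8.3.4, whose heading promises the period and frequency of event assessment, contains only reporting deadlines that run from when the study learns of an event. Section 9.4.4 (Safety Analyses) is marked NA. The models in 9.4.1, 9.4.2 and 9.4.9 cover primary and exploratory outcomes only.

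**The concern.** The exercise risks named in 2.3.1 arise mainly during the 16 weeks of training, and most of that period lies between two AE ticks. A 48-hour reporting clock does not help with an event nobody has asked about. Mild and moderate injuries, soreness and skin reactions would then be recorded only if the participant volunteers them, or recalls them at Measurement 2 up to about 17 weeks later.

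The volunteered route may also differ by arm. Participants and coaches are unblinded (6.3), and one arm has an extra daily channel to staff. A difference in raw AE counts could therefore reflect ease of reporting, or ease of reporting could mask a real difference.

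Severity and relatedness are to be graded under 8.3.3, but the statistical section plans no use of those grades. At stake is whether a trial that aims to raise activity in adults over 60 can give an interpretable account of harms in each arm.

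**Working it through.** The plan states no figure to reproduce; the check is day arithmetic on the visit windows in 1.3. The shortest gap is the earliest next visit minus the latest previous visit. The longest is the latest next visit minus the earliest previous visit.

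**Virtual visit (Day 7–14) to Measurement 2 (Day 120–130)**
- Shortest: 120 − 14 = 106 days.
- Longest: 130 − 7 = 123 days (123/7 = 17.6 weeks).

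**Share of the exercise programme in that gap.** The programme lasts 16 × 7 = 112 days, with 16 × 2 = 32 sessions. No start day is given, so three are assumed.
- Start Day 1, end Day 112: 112 − 14 = 98 to 112 − 7 = 105 days, i.e. 98/112 = 88% to 105/112 = 94%. One to two weeks (2–4 sessions) precede the virtual visit, leaving 28–30 of 32 sessions in the gap.
- Start Day 7, end Day 118: 118 − 14 = 104 to 118 − 7 = 111 days (93–99%).
- Start Day 14, end Day 125: at least 120 − 14 = 106 days, because an early Measurement 2 precedes the last 5 days; at most all 112 (95–100%).

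A later start raises the share, so Day 1 is the mildest of the three cases.

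**Measurement 2 to the final measurement.** This depends on which final date is meant.
- Day 240–250 (1.3): 240 − 130 = 110 to 250 − 120 = 130 days.
- Week 24, i.e. 24 × 7 = Day 168 (one reading of the synopsis and 6.1.1): 168 − 130 = 38 to 168 − 120 = 48 days.

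Section 8.1 says month 6, and the synopsis gives participant duration as 6.5 months. Neither fits Day 240–250.

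**Monitor weeks.** Monitors are issued after the measurement visit. On the dates in 1.3, the third wear week ends around Day 240 + 7 = 247 to 250 + 7 = 257, after the last AE tick if that tick belongs to the visit itself. The second wear week ends 7 days after Measurement 2, so the wait to the next tick is 103–123 days on the dates in 1.3, or 31–41 days on week 24.

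**Other places where an enquiry might sit**
- 6.2.1: the weekly training checklist is listed for fidelity; no AE item is stated.
- 8.2: participants are told to speak up if tired or uncomfortable during a session; AE recording is not mentioned.
- 8.1: monitor collection is described without an AE question.
- 10.1.6: the Safety Officer meets the PI twice a year to review standardized reports; no tabulation by arm is described.

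**What 23 per arm can show.** With assumed event rates, a two-sided Fisher exact test at 0.05 has power of about 9% for 10% against 20%, and about 30% for 10% against 30%.

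**The case against.** The strongest reply is that the gap is in scheduled enquiry, not in contact. Both arms see a trainer twice a week and both have wrist-sensor exchanges. A reader might infer that controls are out of touch with staff between visits; the documents do not support that. The arms differ only in the added messages, which 8.1 says staff may send and which concern activity rather than symptoms. Differential reporting is plausible, not certain.

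The schedule has no column for training sessions, so it could not show a tick there. The checklist's contents are not given, and the Data and Safety Monitoring Plan cited in 10.1.6 is a separate document that was not available. Section 8.3.3.2 asks that doubtful observations be recorded, sections 7.1 and 7.2 require recording of serious illness, non-accidental injurious falls and hospitalization, and the team meets weekly (6.2.1). It would therefore be wrong to say that events in the gap will go unrecorded. What stands is that no section commits staff to ask.

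On tape reactions, 8.2 excludes people with skin allergy or sensitivity to tape, and by the third wear participants will have worn the tape twice before, so the residual risk is smaller. A reader might also infer that a late reaction can never be picked up. Staff do return for the device, and the Measurement 3 window may have been meant to include the wear week, although the order described in 8.1 points the other way.

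Finally, this is a small Stage 1A trial with risks described as minimal. That is a fair argument against a formal safety test, but not against asking and tabulating.

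**Conclusion.** The point holds as a gap in scheduled AE enquiry together with the absence of any planned safety summary. The 106–123 days follow directly from the windows in 1.3 and need no assumption. The 88–94% share assumes training starts on Day 1; later starts make it larger.

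Two parts are conditional. The gap after Measurement 2 is 110–130 days on the dates in 1.3 but about 38–48 days if the final measurement is at week 24, so the longer figure should not be taken as settled. The synopsis, 1.3, 6.1.1 and 8.1 must be reconciled. That the last wear week falls after the last AE tick rests on the tick belonging to the visit at which monitors are issued.

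A reader might conclude that better collection would let the trial show whether Companion adds injuries. It would not: 23 per arm is too few, as the power figures show. The gain is a fair description of harms by arm, collected in the same way in both. This is a worthwhile and cheap improvement; it does not threaten the primary analysis.

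**What to change.** - In 1.3 and 8.3.4, state the enquiry frequency. Add one AE question, worded identically in both arms, to the existing training checklist at every supervised session. Ask it again when staff collect the thigh monitor after each wear week, including the last.
- Flag events volunteered only through a Companion message, so that they can be shown separately.
- Replace NA in 9.4.4 with a descriptive table of AEs and serious AEs by arm, severity and relatedness. Use the solicited events for the between-arm description, with no formal test.
- Reconcile the timing of the final measurement across the synopsis, 1.3, 6.1.1 and 8.1, and say whether the Measurement 3 window includes the wear week.

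The cost is about a minute at contacts that already take place, one line on an existing form and one table. The downside is more minor events to log.
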